14.8.1 IPSS¹

The IPSS is a standardized, validated, and reliable self-administered questionnaire that utilizes 7 questions to assess the frequency and severity of a subject's obstructive and irritative symptoms, with each question scored on a scale of 0 (not at all) to 5 (almost always). Total scores on the IPSS can range from 0-35; a score of 7 or less represents subjects with mild symptoms; 8-19 represents those with moderate symptoms; and subjects with scores from 20-35 typically have severe symptoms.

14.8.2 IIEF²

The IIEF is a validated self-administered questionnaire designed for detecting treatment-related responses in patients with erectile dysfunction. In addition, the IIEF provides a broad measure of sexual function.

14.8.3 MSHQ-EjD Short Form³

The MSHQ-EjD Short Form is a self-administered questionnaire designed to assess ejaculatory dysfunction. The questionnaire consists of three ejaculatory function questions and one ejaculation bother question.

14.8.4 BPH Impact Index⁴

The BPH Impact Index is a self-administered questionnaire that measures the impact of BPH symptoms on the subjects' quality of life. The questionnaire assesses the extent to which the symptoms cause physical discomfort, anxiety/worry, bothersomeness, or otherwise affect activities of daily living.

14.8.5 EQ5D^{™5}

EQ-5D is a standardized instrument used to measure health outcomes. The EQ-5D is a self-reported generic preference-based measure of health, developed by the EuroQol Group. The instrument can be applied to, and has been shown to be valid for, a wide range of health conditions. The EQ-5D has been used in many studies as a way of capturing the health-related quality of life of patients, trial participants and the general public.

14.8.6 Subject Satisfaction Questionnaire

This questionnaire is specific to the NxThera Rezūm System treatment and will measure overall satisfaction with the procedure, recommendation of treatment to friends/family and if the subject would undergo the treatment again if symptoms were to recur after 5 years.

14.8.7 Magnetic Resonance Imaging (MRI) with Gadolinium:

MRI T2 imaging, with dynamic gadolinium enhancement, will be performed on all subjects one week following the study treatment. Size and location of gadolinium defects will be independently assessed using Analyze[®] imaging software, a multi-dimensional, biomedical image display and analysis application.

14.8.8 Necropsy and TTC Stain

For Phase 1 of this study, gross necropsy will begin by placing the treated prostate specimen on a board for closer visual and tactile observation, measurements and pictures. Digital pictures will be taken of the treated prostate, and the prostate then will be sliced serially and the slices exposed for visual observation and digital documentation. Each of these tissue slices then will be submerged into tetrazolium hydrochloride to enhance the visual distinction between treated and untreated tissue. Treatment volume will be estimated from these slices. Observation and measurements will be recorded on the data sheets for each specimen. The sliced, stained tissues will be placed in formalin for the pathology histology examination.

14.8.9 Post Void Residual (PVR)

PVR will be determined using abdominal ultrasound, bladder scanner, or in/out catheterization. Prior to the enrollment of any subject, the study machine at each site will be identified and its accuracy verified.

14.8.10 Uroflow

The uroflow meter parameters will be measured using the uroflow meter. The print-out of the uroflowmeter must be sent to Libra Medical for adjudication.

14.8.11 Prostate Size:

For Phase 1, the extirpated prostate tissue mass/volume will be determined by submerging the treated prostate in isotonic saline in a graduated cylinder or a weight scale.

14.8.12 Transrectal ultrasound (TRUS)

For Phase 2; a TRUS will be performed on each subject during screening prior to treatment in order to obtain the subject's prostate dimensions and assist the PI in the development of each subject's treatment plan. TRUS also will be used to monitor the subject's prostate size at the follow up.

14.8.13 Urinary Tract Infection (UTI) Assessment:

UTI assessment data will be collected per normal laboratory standards. Investigators may conduct a urinalysis using a standard dipstick or may send a urine sample to the laboratory for culture.

14.8.14 Wong Baker Pain Scale

The Wong Baker scale is a validated measurement instrument intended to measure the amount of pain that a patient feels which ranges across a continuum from none to an extreme amount of pain. The pain scale is shown in pictorial form instead of a line. Each subject selects the response that he feels best represents his perception of his then current pain level.

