Purpose:	To evaluate the effect of the NxThera BPH Rezūm System on prostate tissue in subjects suffering from LUTS symptoms secondary to benign prostatic hyperplasia (BPH).
Study Design:	
This study is a single center study. It will be carried out in two phases on subjects with benign prostatic hyperplasia.
 
Phase 1: Acute study - In-vivo treatment of the prostate in subjects scheduled to have a surgical TURP or full excision of the prostate. Prostate tissue will be excised after treatment as part of the planned surgery. There is no follow up.
 
Phase 2: Optimization study - Subjects with BPH symptoms will be treated with the Rezūm device with a range of thermal energies (as measured by calorie output) to optimize the setting for maximum lesion size with minimal intra and post procedure discomfort. The lesion size and ablated tissue resorption rate will be followed post-procedure via MRIs.

Enrollment:	
Phase 1: Up to 20 BPH subjects scheduled for surgical removal of the BPH tissue
 
Phase 2: Up to 15 BPH subjects suffering from BPH symptoms.

Target Subject Population:	
 • Male subjects \geq 45 years of age who have symptomatic / obstructive symptoms secondary to BPH requiring surgical intervention.
Follow-up:	
Phase 1 – Acute, no follow up
 
Phase 2 – 1 day, 1 week, 1 month, 3 months, 6 months, 12 months, and annually thereafter up to 5 years.

Phase 1 Endpoint	Lesion size and characteristics as evaluated using Tetrazolium Chloride (TTC) stain and histopathologic evaluation of representative samples.
Phase 2 Endpoints	
Lesion characterization via MRI
 
Intra and post procedure discomfort
 
Catheterization post procedure
 
The change (improvement) from baseline in International Prostate Symptom Scores (IPSS) at day 1, week 1, month 1, months 3,6 and 12, and annually thereafter up to 5 years

CONFIDENTIAL: Contains Proprietary Information

Study and Data Management:	Libra Medical, Inc. [name] [contact] [contact] Email: [contact]
Study Monitors:	Libra Medical, Inc. [name] [contact] [contact] Email: [contact]
Sponsor:	NxThera Inc [name] [contact]

TABLE OF CONTENTS

1	BACKGROUND.....	8
2	SUMMARY DEVICE DESCRIPTION.....	8
3	SUMMARY OF PROCEDURE	9
4	PHASE I ACUTE STUDY DESIGN.....	12
5	PHASE 2: OPTIMIZATION STUDY	13
6	STUDY PROCEDURES	15

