5.2 STUDY DESIGN

In this Phase 2 study, up to 15 subjects with LUTS secondary to BPH requiring surgical treatment will be treated with the Rezūm System. Treatment is ≤ 10 seconds per treatment. The power and water flow rate settings may be adjusted slightly to minimize pain and swelling to the subjects while maximizing the treatment area (e.g., lesion size). The power setting will be between 175W and 250W with a concomitant adjustment to the water flow rate of 2.7 ml/min to 5.0 ml/min. The actual power output will be recorded. For all the treatment settings, adverse and subject responses will be collected. The range of acceptable power setting have been determined in bench-top, animal studies, testing on extirpated human prostate to create lesions of a size that is adequate to treat the BPH tissue. The unknown factor that will be evaluated in this Phase 2 study is the acute response(s) to the different treatments in terms of procedural and post procedural discomfort. If the subjects are able to tolerate the higher caloric treatments, those treatments will be used in subsequent subjects. If the subjects are not able to tolerate a particular caloric treatment, the lower caloric treatment will be used in subsequent subjects.

The standard Rezūm treatment following the IFU will be followed. Information regarding the vapor needle configuration, treatment settings, treatment medications, pain or discomfort during treatment, post-treatment catheterization requirements, and the type and severity of any short term irritative or urinary obstructive symptoms will be collected. Information regarding the subjects' symptomatic response and uroflowmetry characteristics will be collected at baseline and in follow-up evaluations conducted with each subject. Any adverse events will be evaluated at each visit. Lesion characteristics and treated tissue resorption rate will be measured by gadolinium enhanced MRI imaging techniques performed post-procedure at specified intervals.

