5.3 OPTIMIZATION ENDPOINTS

5.3.1 Endpoint 1: Intra-procedure Pain

Procedural pain will be assessed using the Wong Baker scale. Subjects will be asked to rate the level of pain and discomfort during the treatment.

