5.3.2 Endpoint 2: Post-Procedure Catheterization

All subjects will be kept at the clinic for observation for 24 hours post-procedure. Post procedure catheterization will only be allowed if the Principal Investigator determines that

the subject has symptoms of retention (defined as failure to void within 8 hours post procedure) or requires catheterization for other safety reasons.

5.3.3 Endpoint 3: Lesion size, as measured by MRI at Week 1 post-procedure.

5.3.4 Endpoint 4: Change in IPSS score from baseline at various points post-procedure.

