6.5.1 Scheduled Follow-up Visits

Table 6-2: Schedule of Visits

	Baseline Pre-Op	1 day	1 week	1 month	3 month s	6 month s	1 year	Annual (2-5 years)	Unsched uled
IPSS	√	√	√	√	√	√	√	√	optional
BPH Impact Index	√			√	√	√	√	√	optional
EQ5D	√			√	√	√	√	√	
Sexual function (IIEF)	√			√	√	√	√	√	optional
MSHQ-EjD Short Form	√			√	√	√	√	√	optional
Subject Satisfaction Questionnaire			√	√	√	√	√	√	optional
Subject Pain Assessment		√	√	√	√	√			
Uroflow (Qmax + PVR)	√		√	√	√	√	√		optional
Urodynamics	√								
Prostate specific antigen (PSA)	√				√	√	√	√	
Prostate Volume	√				√	√	√	√	
Cystoscopy	√		√						
MRI	option al		√	√	√	√			
Adverse event(s)		√	√	√	√	√	√	√	√
Medication(s) used	√	√	√	√	√	√	√	√	√

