7.2 STUDY RELATED AE DEFINITION

This section applies particularly to the Phase 2 part of the study. The transurethral intervention with a rigid scope similar in size to the Rezūm device commonly is associated with transient symptoms. For the purpose of this study, these types of transient symptoms will not be considered an adverse event. The corollary to a surgical procedure is bleeding. Bleeding will occur in all surgical BPH procedures, and bleeding, therefore, is not clinically significant and typically not reported as an AE. The following types of signs and symptoms that are attributed to the procedure, last less than or equal to 72 hours, AND do not result in intervention, re-hospitalization, or prolonged unplanned hospitalization, will not be considered AEs.

- Dysuria
- Hematuria
- Storage (irritative) LUTS
- Urgency/frequency
- Nocturia
- Urge incontinence
- Voiding (obstructive) LUTS
- Hesitancy
- Decrease flow
- Increase residual
- Pain/discomfort
- Catheterization

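### Post-procedure discomfort is a Phase 2 endpoint, but no pain rating is scheduled between the treatment itself and the 1-day visit, so first-day discomfort goes unscored.

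*Combined protocol and SAP*

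**What the plan says.** The synopsis gives the Phase 2 aim as lesion size balanced against "intra and post procedure discomfort" and lists discomfort during and after the procedure among the endpoints. Section 5.1 repeats the aim. Section 5.2 identifies the open question as the "acute response(s) to the different treatments in terms of procedural and post procedural discomfort".

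The measurement provisions are these:

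- **During treatment (5.3.1):** Wong Baker is used. "Subjects will be asked to rate the level of pain and discomfort during the treatment".
- **First day (5.3.2):** "All subjects will be kept at the clinic for observation for 24 hours post-procedure". No pain rating is attached to this stay.
- **After that (Tables 6-1 and 6-2):** the first pain assessment is at the 1-day visit, followed by 1 week, 1 month and later visits. Table 6-2 labels the row "Subject Pain Assessment" and has no procedure-day column. Neither table names an instrument or a recall period.
- **Scale (14.8.14):** "Each subject selects the response that he feels best represents his perception of his then current pain level".
- **Adverse events (7.2):** listed symptoms attributed to the procedure, pain among them, that "last less than or equal to 72 hours, AND do not result in intervention, re-hospitalization, or prolonged unplanned hospitalization, will not be considered AEs".

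Section 5.3 defines intra-procedure pain as an endpoint but contains no definition of post-procedure discomfort.

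**The concern.** A score of pain at the moment of rating says nothing about the hours before it. If the first such score after treatment comes at day 1 to 2, discomfort during the preceding day is recorded nowhere as a pain score. The adverse event forms do not fill the gap, because short, uncomplicated procedure pain is excluded from them by definition.

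What is at stake is one side of the trade-off that Phase 2 was set up to describe. If two settings differ in discomfort mainly in the first hours, the scheduled scores will show less of that difference than the subjects experienced. The missing scores cannot be recovered later, and every subject is in the clinic while they could be taken.

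**Working it through.** The plan gives no figure to reproduce. It states no expected pain level, standard deviation, difference between settings or power; Phase 2 enrols up to 15 subjects and section 14.2 provides for descriptive statistics only. The check has two parts.

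**1. Schedule against endpoint**

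| Period | Scheduled pain score | Source |
|---|---|---|
| During treatment | Yes, Wong Baker | 5.3.1 |
| End of treatment to 1-day visit, including the 24-hour stay | None | 5.3.2, Tables 6-1 and 6-2 |
| 1-day visit (1 to 2 days) | Yes, instrument not named | Tables 6-1 and 6-2 |
| Week 1 (days 4 to 7) and later | Yes, instrument not named | Tables 6-1 and 6-2 |

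Reading the 1-day window as 24 to 48 hours, the scheduled gap is about 24 to 48 hours and covers the clinic stay up to its end. No item looks back over it.

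**2. How much of an early difference could be left (illustration)**

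Assumptions, none of them in the documents: pain falls exponentially from the end of treatment, with the same half-life h at each setting, and h lies between 12 and 48 hours. The fraction of an initial between-setting difference remaining at time t is then 0.5^(t/h).

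| Half-life | 24 h | 48 h | 96 h (start of week 1 window) |
|---|---|---|---|
| 12 h | 0.5^2 = 25% | 0.5^4 = 6% | 0.5^8 = 0.4% |
| 24 h | 0.5^1 = 50% | 0.5^2 = 25% | 0.5^4 = 6% |
| 48 h | 0.5^0.5 = 71% | 0.5^1 = 50% | 0.5^2 = 25% |

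An initial difference of 2 points (also assumed) would appear at 24 hours as 2 × 0.25 = 0.5, 2 × 0.50 = 1.0 or 2 × 0.71 = 1.4 points. At 48 hours it would appear as 2 × 0.0625 = 0.1, 2 × 0.25 = 0.5 or 2 × 0.50 = 1.0 points. By week 1 it is at most 2 × 0.25 = 0.5 points, so the later visits do not make up for the gap.

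Under the same assumptions, a subject rated at 24 hours instead of 48 hours scores 0.5^(24/h) / 0.5^(48/h) = 2^(24/h) times as high: 4.0, 2.0 or 1.4 for h = 12, 24 or 48 hours. The actual time of rating therefore needs to be recorded alongside the visit label.

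**The case against.** The strongest case on the other side has four parts.

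- **Instrument.** Wong Baker is tied by name only to procedural pain. Section 5.3.1 uses it for pain during treatment, so the present-moment wording in 14.8.14 may not be a strict recall rule. This stands as a caveat: its use at follow-up is an inference, resting on the fact that no other pain scale is described. It is also a reason to name the instrument.
- **Other early data.** Section 5.2 calls for adverse and subject responses at every setting, catheterization needs, and short-term urinary symptoms with their severity. IPSS and medications are recorded at day 1. This also stands. These bear on early discomfort by setting, but none is a timed pain score, and section 5.2 gives no instrument or time for pain after treatment.
- **Choice of setting.** A reader might infer that a poorly tolerated setting would be accepted because its pain had eased by day 1. The documents do not support that. The rule is "If the subjects are able to tolerate the higher caloric treatments, those treatments will be used in subsequent subjects", and it is not tied to the day 1 score. Clear intolerance would be seen during the stay, and pain leading to intervention or prolonged unplanned hospitalization is not exempt from adverse event reporting.
- **Course of pain.** A reader might also infer that peak pain is missed and that settings would look alike. The documents do not say when pain peaks. Swelling is mentioned in 5.2, and a course that rises before it falls would change every figure above. The 1-day visit might also coincide with discharge, and pain during treatment can still separate settings.

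Finally, with up to 15 subjects, settings adjusted in sequence, discretionary pain killers (6.4) and descriptive analysis, any comparison of pain between settings will be rough however often pain is rated. That limits what the fix can deliver. It does not justify leaving the first day of a named endpoint unscored.

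**Conclusion.** The point holds as a gap in measurement. Discomfort between the end of treatment and the 1-day visit has no scheduled score and no look-back item, although post-procedure discomfort is an endpoint and part of the question Phase 2 asks. A difference between settings that fades by day 1 to 2 would be understated.

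The amount is unknown. The range of about 6% to 71% remaining at 24 to 48 hours rests wholly on assumed exponential decay with a half-life of 12 to 48 hours, and on reading the window as hours and not calendar days. The finding does not extend to a claim that settings will be indistinguishable or that the tolerance rule will fail. It is a worthwhile, inexpensive improvement.

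**What to change.** In section 14.8.14 and Tables 6-1 and 6-2:

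1. Name Wong Baker as the instrument for the follow-up pain assessments and state its recall period.
2. Add current-pain ratings at a few fixed times during the 24-hour stay (for example 1, 4, 8 and 24 hours after the procedure).
3. Add one item on the same scale at the 1-day visit asking for worst pain since the procedure.
4. Report these by treatment setting, with the actual time of each rating and any pain medication taken, alongside the existing visit scores.

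The cost is a few more self-ratings on an existing scale while subjects are already present, and one item that relies on short recall. Redefining the endpoint as the maximum score to week 1 is optional: a maximum depends on how many ratings are taken, and early scores may partly reflect retention or catheter discomfort.

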14.9 SUSPENSION OR EARLY TERMINATION OF THE CLINICAL INVESTIGATION

If the clinical study is terminated prematurely or suspended, NxThera, as Sponsor, will promptly inform the Principal Investigator of such termination or suspension, and the reason(s) for this decision. The EC also shall be informed promptly and provided with the reason(s) for the termination or suspension by the Sponsor or by the Principal Investigator.

